## **9.5. Eyelid Sulcus, Eyelid, Eyelash, and Iris Color**

For changes from baseline in eyelid pigmentation, eyelid hair growth, eyelash length, eyelash thickness, eyelash pigmentation, eyelash number, and iris color/pigmentation, frequency and percentage of subjects with No change, Increased, or Decreased will be summarized by treatment, analysis visit, and study period (double masked and open-label) for study eyes and for fellow eyes. For changes from baseline in eyelid sulcus, count and percentage of changes (Yes) will be summarized by treatment and analysis visit (Month 3, Month 6, Month 9, and Month 12) for study eyes and for fellow eyes. In addition, any changes from baseline in eyelid sulcus will be listed.

## **9.6. Vital Signs**

Resting blood pressure (systolic and diastolic) and pulse rate and their change from baseline will be summarized by treatment, analysis visit, and study period (double masked and open-label).

A listing for vital signs will be provided.

## **10. ADDITIONS AND CHANGES TO THE PROTOCOL-SPECIFIED ANALYSES**

### **10.1. Full Analysis Set Definition**

The full analysis set definition has been updated to add the requirement that baseline IOP data has to be present:

The Full Analysis Set (FAS) will include all randomized subjects who received at least one dose of study medication and provided Baseline IOP data (at any timepoint) and at least one post-baseline IOP measurement (at any timepoint). Efficacy analyses will be performed using the FAS and summarized by treatment as randomized.

### **10.2. Key Secondary Endpoint**

An additional key secondary endpoint (IOP at each scheduled timepoint [08:00, 10:00, and 16:00] at Week 1 [Visit 3], Week 6 [Visit 4], and Month 3 [Visit 5] in the study eyes with mean diurnal IOP < 25 mmHg at the Baseline Visit) was added based on analysis results of a recently completed study in Asia. This key secondary endpoint was not in the clinical study protocol, but instead it was added in the SAP. All endpoints for this study are presented in [Section 2.2](#).

### **10.3. Sensitivity Analysis of the Primary and Secondary Efficacy Endpoints**

Protocol Amendment 1 (Version 1.1) Section 14.5, Handling of Missing Values, specified a sensitivity analysis of the primary efficacy endpoints and the secondary binary IOP endpoints (Month 3) in which missing values would be imputed using the last-observation-carried-forward (LOCF) approach. The LOCF approach is removed from the sensitivity analyses because the PMM generalizes the MMRM to include mixed missing data mechanisms beyond the MAR assumption of the MMRM. Thus, the PMM is sufficient to evaluate the robustness of the results from the MMRM.

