14.4.2. Full Analysis Set

The Full Analysis Set (FAS) will include all randomized subjects who received at least one dose of study medication and provided at least one post-baseline IOP measurement. The efficacy analysis will be performed on the FAS or a subset of the FAS by planned treatment.

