14.5. Handling of Missing Values

The primary analysis of continuous IOP endpoints will be performed using the MMRM analysis on observed cases. As sensitivity analyses, a last-observation-carried-forward (LOCF) approach and a Pattern Mixture Models (PMM) approach may be applied to evaluate the impact of missing data on the primary analysis results. For the binary IOP endpoints, the missing data at Month 3 will be imputed using an LOCF approach.

For medical events including AEs and medical history, completely or partially missing onset and resolution dates will be imputed in a conservative fashion. Same rules will be followed to impute the completely or partially missing start and end dates of non-study medications.

Unless specified otherwise, descriptive summaries will be based on observed cases.

More details on handling of missing data will be provided in the SAP.

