14.7. Efficacy Analyses

Unless specified otherwise, for subjects who discontinue from the study medication per protocol before the Study Exit, the IOP data collected after the study medication discontinuation with any use of non-study IOP lowering medication or surgery will be censored from all efficacy analyses.

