**Table 5: Response Endpoints**

| Response Endpoint           | Response criteria in mean diurnal IOP       |
|-----------------------------|---|
| IOP 20% response            | Percent reduction from Baseline $\geq 20\%$ |
| IOP 25% response            | Percent reduction from Baseline $\geq 25\%$ |
| IOP 30% response            | Percent reduction from Baseline $\geq 30\%$ |
| IOP $\leq 18$ mmHg response | Mean diurnal IOP $\leq 18$ mmHg             |

For a response endpoint, the response rate at a post-Baseline visit is calculated as the proportion of subjects who met the response criterion at the post-baseline visit.

The open-label analysis of these endpoints will be performed only at the end of this study when all adult subjects complete their Month 12 Visit.

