### **5.3. Full Analysis Set**

The Full Analysis Set (FAS) will include all randomized subjects who received at least one dose of study medication and provided Baseline IOP data (at any timepoint) and at least one post-baseline IOP measurement (at any timepoint). Efficacy analyses will be performed using the FAS and summarized by treatment as randomized.

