## 6.2. Handling of Missing Data

### 6.2.1. Efficacy Measures

For subjects with the use of any non-study IOP-lowering therapy to lower IOP, unless otherwise specified, the IOP data collected after the non-study IOP-lowering therapy will be censored (treated as missing) in efficacy analyses in both double-masked and open-label periods.

For efficacy measures during double-masked period,

- For each IOP endpoint, no imputation is needed for the analysis on observed cases using the mixed-effects model for repeated measures (MMRM). Sensitivity analysis will be performed using a Pattern-Mixture Model (PMM) approach.
- In the PMM approach, Multiple Imputation (MI) with mixed missing data mechanisms will be used to investigate the appropriateness of the missing at random (MAR) assumption for missing values resulting from censoring due to the use of IOP-lowering rescue therapy, or resulting from study discontinuation due to lack of efficacy or AE.

For efficacy measures during open-label treatment period, no inferential analysis will be performed. Summary statistics will be provided for IOP and mean diurnal IOP for each scheduled visit, using observed data.

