## 8. EFFICACY ANALYSES

Unless specified otherwise, efficacy analyses will be performed on the study eye, based on the FAS, and summarized by planned treatment, irrespective of the actual treatment received.

Unless otherwise specified, for subjects who receive IOP-lowering rescue therapy, any IOP values collected after the receipt of rescue therapy will be censored (i.e., treated as missing) in the analyses.

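### SAP 10.3 drops the protocol's Month 3 missing-data rule for the responder endpoints for a reason that applies only to the MMRM, and states no rule or denominator in its place

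*SAP*

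**What the plan says.** Protocol 14.5 contains two separate rules. One allows LOCF and a PMM as optional sensitivity analyses of the primary result. The other stands in its own sentence and is mandatory: "For the binary IOP endpoints, the missing data at Month 3 will be imputed using an LOCF approach".

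SAP 10.3 reports that the protocol specified LOCF as a sensitivity analysis for both the primary and the binary endpoints, and removes it: "The LOCF approach is removed from the sensitivity analyses because the PMM generalizes the MMRM". It concludes that the PMM is enough to judge the robustness of the MMRM results.

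The other relevant places are:

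- **Test.** SAP 8.1.2 compares the responder rates by Pearson chi-square at each post-baseline visit. It states the rescue rule for the MMRM and for summaries of raw scores, and no missing-data rule for the chi-square tests.
- **Rate.** SAP 4.3.1 says the response rate is "calculated as the proportion of subjects who met the response criterion at the post-baseline visit". It does not say which subjects form the denominator.
- **Censoring, protocol.** Section 14.7 covers subjects who discontinue study medication. Their IOP collected afterwards "with any use of non-study IOP lowering medication or surgery will be censored from all efficacy analyses".
- **Censoring, SAP.** Section 8 covers any subject who receives rescue: "any IOP values collected after the receipt of rescue therapy will be censored (i.e., treated as missing) in the analyses". Section 6.2.1 says the same of any non-study IOP-lowering therapy.
- **Population.** Protocol 14.4.2 admits to the FAS treated subjects who "provided at least one post-baseline IOP measurement". SAP 5.3 adds a baseline value.

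**The concern.** SAP section 10 exists to record departures from the protocol. Here it describes a handling rule as a sensitivity analysis, and then justifies removing it with an argument about a different model. What remains for four responder criteria at three double-masked visits is a set of tests with p-values and no stated treatment of missing data.

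What is at stake is who is counted. A subject who needs additional IOP-lowering therapy, or leaves because the drug did not work or was not tolerated, is unlikely to be the typical responder. If such subjects vanish from the denominator, the reported rates describe those who did well enough to stay. If they vanish more often in one arm, the comparison is affected too.

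**Working it through.** The plan gives no figure for this point, so there is none to reproduce. The check is a comparison of passages, followed by an illustration with assumed inputs.

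**Step 1: does the reason in SAP 10.3 fit?** The PMM in SAP 8.1.1.2 is planned for the primary and key secondary endpoints. Its step c re-fits the primary MMRM to each imputed dataset. The responder endpoints are other secondary endpoints tested by chi-square. No planned PMM output bears on them.

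**Step 2: is there a replacement rule?** SAP 6.2.1 dispenses with imputation only for the MMRM. Sections 4.3.1 and 8.1.2 are silent. Appendices A and B are not in the available text, but SAP 8.1.1.2 describes them as MMRM and PMM code, so they would not be expected to fill the gap. Observed cases is the natural inference. It remains an inference, because SAP 8 bases efficacy analyses on the FAS, and a proportion of subjects could also be read over all of the FAS.

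**Step 3: who is counted at Month 3?** FAS membership requires a post-baseline IOP value, so nearly every FAS subject had something to carry forward.

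| Subject | Protocol 14.5 and 14.7 | SAP, most likely reading |
|---|---|---|
| Stopped study drug, then used other IOP-lowering therapy | Later IOP censored, earlier value carried, counted | Censored, not counted |
| Used other IOP-lowering therapy while on study drug | Month 3 value kept, counted | Censored, not counted |
| Left the study for lack of efficacy or AE | Earlier value carried, counted | No value, not counted |
| Stopped study drug, no other therapy, kept attending | Observed, counted | Observed, counted |

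Rows 1 and 3 change because LOCF is removed. Row 2 changes because the SAP widens the censoring. SAP 10.3 does not address that widening.

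**Step 4: how large could the LOCF change be?** All inputs are assumed: r is response among observed subjects (equal in both arms), mT and mC are the missing shares on DE-117 and Timolol, and q is response among carried-forward values.

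- Observed-case difference = r - r = 0.
- LOCF rate in an arm = (1 - m)r + mq.
- LOCF difference = -(mT - mC)(r - q).

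With r = 50%, mT = 8%, mC = 3%:

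| q | LOCF rate, DE-117 | LOCF rate, Timolol | Difference (points) |
|---|---|---|---|
| 0% | 46.0% | 48.5% | -2.5 |
| 25% | 48.0% | 49.25% | -1.25 |
| 50% | 50.0% | 50.0% | 0 |
| 75% | 52.0% | 50.75% | +1.25 |

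The sign turns on whether carried values respond less or more often than observed ones. With equal missing shares the difference does not move. Within an arm, the observed-case rate exceeds the LOCF rate by m(r - q): 4.0 and 1.5 points at q = 0%, and -2.0 and -0.75 points at q = 75%.

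**The case against.** The strongest reply has four parts.

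- **Disclosure.** SAP 10.3 states openly that LOCF is removed and names the Month 3 binary endpoints, and Protocol 14.5 defers missing-data detail to the SAP. This stands. A reader might infer that the change was hidden, and the documents do not support that. The fault is the description of the rule and the reason for dropping it.
- **Observed cases are implied.** Once LOCF goes and nothing else is named, observed cases remain. As the likely intent, this stands. It does not settle the denominator in 4.3.1, and it confirms that rescued subjects would leave it.
- **Cause.** A reader might attribute every lost rescued subject to the removal of LOCF. That is too strong. Protocol 14.7 censors only after study drug discontinuation, so a subject rescued while on study drug kept the observed value, and that loss comes from the wider censoring in SAP 6.2.1 and 8.
- **Size.** Subjects who leave for an adverse event may have responded, so q can exceed r and the shift can go either way. With about 200 per arm at 50% response, the standard error of the difference is about sqrt(0.5 x 0.5 x 2/200) = 5 points, so a 2.5-point shift is half a standard error. This stands: the documents do not show that the change favours DE-117.

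LOCF was also never a failure rule, and it covered Month 3 only. Weeks 1 and 6 had no rule for the binary endpoints in either document.

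**Conclusion.** The point holds as a gap in a secondary analysis. The protocol's handling rule for the binary endpoints is misdescribed and removed for a reason that does not apply to them, and nothing replaces it. As written, the plan most likely drops rescued subjects, and those who leave for lack of efficacy or AE, from the responder rates. This can overstate response, and can bias the arm difference if those losses differ by arm.

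The size and sign cannot be known from the documents. The range of -2.5 to +1.25 points rests on an assumed 50% response, 8% vs 3% missing and 0% to 75% response among carried values. It covers the LOCF change only, not the wider censoring.

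A reader might take this as a threat to the main result. It is not: the responder endpoints lie outside the seven-test sequence in SAP 6.4, so the primary and key secondary conclusions and Type I error control are unaffected. The change should still be made, because it is cheap and the rule should be fixed before unmasking.

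**What to change.** In SAP 4.3.1 and 8.1.2, keep the Pearson chi-square test and add:

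1. An FAS subject whose mean diurnal IOP at a double-masked visit is censored for IOP-lowering rescue, or missing after study discontinuation for lack of efficacy or AE, stays in the denominator and counts as not meeting the criterion. These are the categories the SAP already uses in PMM step b.
2. Values missing for any other reason, including a visit without all three readings, are excluded as in an observed-case analysis.
3. An analysis over all FAS subjects, with every missing value counted as not met, is reported as supportive.

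In SAP 10.3, state that the protocol's handling rule for the binary endpoints has been replaced, and give a reason that applies to them.

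The cost is a few SAP sentences and one supportive analysis with the same test; no imputation model is needed. Reported rates become slightly lower. Under the assumptions above, if all missing values fell in the first group, the rates would be 0.5 x 0.92 = 46.0% and 0.5 x 0.97 = 48.5% instead of 50%, a drop of 4.0 and 1.5 points. That is the effect of the proposed rule, not of the SAP's change from LOCF.

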## **12. APPENDICES**
